The randomized groups will be descriptively compared on baseline demographic and pain variables using descriptive statistics. In particular, groups will be considered well-balanced on a particular baseline variable if the standardized difference (difference in means or proportions divided by the pooled standard deviation) is less than $\sqrt{2/n}$, where *n* is the per-group sample size.¹⁰³ The primary analysis will be modified intention-to-treat, in which all randomized subjects who received any of the study treatment will be included and retained in their respective treatment groups.¹⁰⁴

Hypothesis 1: Primary outcome. We will assess the average causal effect of ambulatory CPNB versus placebo on phantom limb pain intensity (average pain over past 72 hours) at 4 weeks after the initial perineural catheter insertion and subsequent infusion using analysis of covariance to adjust for baseline pain intensity and any imbalanced baseline variables (see above). Results will be summarized as the least squares difference in means at 4 weeks and 95% confidence interval. Mean and standard deviation change from baseline intensity will also be summarized. Similar analyses will be conducted for the secondary outcomes of current/present, worst and least phantom pain, as well as average and worst residual limb pain.

Secondary outcomes.

Hypothesis 2a. The randomized groups will be compared on the global measure of improvement (Patient Global Impression of Change Scale) at 4 weeks using the Mann-Whitney test. Proportional odds logistic regression will be used to adjust for any imbalanced baseline variables, as appropriate.

Hypothesis 2b. The randomized groups will also be compared at 4 weeks on the seven measures of Brief Pain Inventory which evaluate pain's interference with physical and emotional functioning. We will use a mixed effects multivariate model (random subject term, fixed treatment effect, unstructured correlation matrix) to first assess whether the treatment effect differs across the 7 measures (i.e., treatment-measure interaction). In presence of an interaction, each measure will be evaluated univariably. Otherwise, an overall treatment effect will be estimated from the mixed effects model as the primary result for this aim.

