Interim analyses. We will conduct interim analyses to assess efficacy (rejecting null) and futility (rejecting alternative) at each 25% of the maximum enrollment using a group sequential procedure. Specifically, a gamma spending function will be used with parameters -4 and -2 for efficacy and futility, respectively.¹⁰⁵ Thus, boundaries at the 1st through 4th analyses for efficacy (futility in parentheses) will be P \leq 0.0016 (P>0.9572), P \leq 0.0048 (P>0.7186), P \leq 0.0147 (P>0.2389) and P \leq 0.0440 (P>0.0440), Figures 7 and 8.

Figure 7. Boundaries for efficacy and futility.

Figure 8. Alpha and beta spending functions

Type I error. We will use a parallel gatekeeping procedure to control the study-wide type I error at 0.05.¹⁰⁶ For this procedure we therefore a priori prioritize the study outcomes into ordered sets, as Aim 1, Aim 2a, Aim 2b and then Aim 2c. Analysis will proceed in that order, and testing will proceed through each "gate" to the next set if and only if at least one outcome in the current set reaches significance. The significance level for each set will be 0.05 times a cumulative penalty for non-significant results in previous sets (i.e., a "rejection gain factor" equal to the cumulative product of the proportion of significant tests across the preceding sets). Within a set, a multiple comparison procedure (Bonferroni correction) will be used as appropriate to control the type I error at the appropriate level. SAS statistical software (Carey, North Carolina), R programming language (The R Project for Statistical Computing) and East 5.3 software (Cytel Inc.) will be used for all analyses.

Sample size considerations. Our sample size estimate is based on the primary specific aim of whether the addition of an ambulatory CPNB decreases phantom limb pain intensity resulting from a traumatic amputation compared with current standard-of-care treatment at 4 weeks following the ambulatory CPNB. Receiver operating characteristic curve analyses demonstrate that changes from baseline of at least 1.7 along a 10-point NRS accurately identified patients who rated improvements as "much improved" or more, compared with those who perceived no change or worsening following analgesic interventions.⁸⁸ Multiple additional studies confirm this degree of reduction as clinically meaningful to individual patients with chronic pain.^{85,107,108}

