Therefore, we power our study to be able to detect group differences in mean change from baseline of 1.7 points or more on the NRS. Based on a conservative standard deviation estimate for each group of 3.0 at 28 days, a correlation of 0.50 between baseline and follow-up NRS, a two-sided test at the 0.05 significance level, power of 0.90, and 4 equally spaced analyses (3 interim and 1 final, as needed), a maximum of 72 subjects in each group (N=144 total) is required (East 5.3 software, Cytel Inc). The expected sample size for this group sequential design (i.e., average sample size over thousands of such trials, stopping when a boundary is crossed) is a total of 100 under the alternative and 102 under the null hypotheses. Table 2 reports boundary crossing probabilities at each of the 4 analyses for this design, assuming that either the null or alternative hypotheses were true. For example, there is a cumulative 8%, 37% and 75% chance of crossing a boundary at the 1st, 2nd, and 3rd analyses, respectively, if the alternative hypothesis were true. However, if the true standard deviation at 28 days were smaller, say 2.5 instead of 3.0, then the cumulative probability of stopping for efficacy at the 1st, 2nd and 3rd analyses, respectively, would increase to 16%, 55% and 88% under the alternative hypothesis.

Fraction of Maximun Accrual		Cumulative Accrual	Alpha Spent	Beta Spent	P-value Bo	oundaries	Boundary Crossing Probabilities		
					HO	H1	Under H0	Under H1	
0.250		36	0.002	0.010	0.0016	0.9572	0.044	0.083	
0.500		72	0.006	0.027	0.0048	0.7186	0.269	0.290	
0.750		108	0.018	0.054	0.0147	0.2389	0.485	0.379	
1.000		144	0.050	0.100	0.0440	0.0440	0.202	0.248	

 Table 2. P-value boundaries and boundary crossing probabilities for group sequential design.

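### The trial stops by a four-look group-sequential rule, but the primary estimate and 95% CI are not adjusted for stopping: near the planned effect the estimate averages about 10% too high and the interval covers 92.5–93.5%

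*Combined protocol and SAP*

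**What the plan says.** All references are to the combined protocol and SAP, Section 9.

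- **Hypothesis 1: Primary outcome.** The groups are compared "using analysis of covariance to adjust for baseline pain intensity and any imbalanced baseline variables (see above"). Then: "Results will be summarized as the least squares difference in means at 4 weeks and 95% confidence interval".
- **Interim analyses.** "We will conduct interim analyses to assess efficacy (rejecting null) and futility (rejecting alternative) at each 25% of the maximum enrollment". The boundaries come from spending functions: "a gamma spending function will be used with parameters -4 and -2 for efficacy and futility, respectively". The printed two-sided efficacy P values are 0.0016, 0.0048, 0.0147 and 0.0440. The futility P values are 0.9572, 0.7186, 0.2389 and 0.0440.
- **Sample size considerations.** The maximum is 144 subjects (72 per group), and early stopping is likely. The stated figures are: "cumulative 8%, 37% and 75% chance of crossing a boundary at the 1st, 2nd, and 3rd analyses, respectively, if the alternative hypothesis were true".
- **Crossover phase.** The average causal effect obtained from the first phase is described as unbiased.

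No section names a bias-adjusted or median-unbiased estimate, a repeated or stopping-adjusted interval, or a final confidence level matched to 0.0440.

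**The concern.** The plan corrects its P values for repeated looks but not the numbers it will report. A trial that stops because its estimate was extreme tends to report an extreme estimate, and an interval computed as if the sample size had been fixed loses its stated coverage. The final critical value is also 2.014 rather than 1.96, so the interval and the test use different thresholds.

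This is the headline result. Readers will set it against the plan's own benchmark: "we power our study to be able to detect group differences in mean change from baseline of 1.7 points or more on the NRS". An average excess of about 0.17–0.18 points, more after a positive conclusion, matters when a result is judged against 1.7. The interval can mislead in the other direction too. After a futility stop at the third look with z = 0.9, the ordinary CI (SD 3.0) is −0.61 to 1.65, which rules out 1.7. The stopping-adjusted CI, −0.49 to 1.85, does not.

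**Working it through.** **Inputs (Sample size considerations; Interim analyses).** Effect 1.7; SD 3.0 per group at 28 days; baseline to follow-up correlation 0.50; two-sided 0.05; power 0.90; looks at 36, 72, 108 and 144 subjects (18, 36, 54 and 72 per arm); printed P boundaries.

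**Two variance scales.**
- Change score: SD = √(9 + 9 − 2 × 0.50 × 9) = 3.0. Full-information SE = 3.0 × √(2/72) = 0.50, so drift = 1.7/0.50 = 3.40.
- ANCOVA, the planned analysis: residual SD = 3.0 × √(1 − 0.50²) = 2.598. SE = 2.598 × √(2/72) = 0.433, so drift = 1.7/0.433 = 3.93.

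**Critical values.** Two-sided P of 0.0016, 0.0048, 0.0147 and 0.0440 correspond to |z| = 3.156, 2.820, 2.440 and 2.014.

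**Reproducing the plan.** Simulating the test statistic as Brownian motion with these boundaries and SD 3.0:

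| Quantity | Plan | Recomputed |
|---|---|---|
| Stopping probabilities, H1 | 0.083 / 0.290 / 0.379 / 0.248 | 0.083 / 0.290 / 0.380 / 0.247 |
| Stopping probabilities, H0 | 0.044 / 0.269 / 0.485 / 0.202 | 0.044 / 0.269 / 0.485 / 0.202 |
| Expected N, H1 / H0 | 100 / 102 | 100.5 / 102.4 |
| Power | 0.90 | 0.90 |

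The design figures hold, and they match the SD 3.0 scale.

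**Ordinary estimate and CI (estimate ± 1.96 SE) at a true effect of 1.7.**

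| | SD 3.0 | ANCOVA SD 2.598 |
|---|---|---|
| Mean estimate | 1.87 | 1.88 |
| Mean given an efficacy conclusion | 2.02 | 1.94 |
| Coverage of the 95% CI | 92.5% | 93.5% |
| CI excludes zero, test does not reject | 0.6% | 0.2% |

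Relative excess: 1.87/1.70 = 1.10; 2.02/1.70 = 1.19; 1.94/1.70 = 1.14. A patient-level ANCOVA simulation with t-based intervals gives a mean of 1.86 and coverage of 93.4%. The same ANCOVA without interim looks gives 95.0%, so the loss comes from stopping.

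**Other true effects (SD 3.0).** At zero: bias 0, coverage 95.0%, rejection rate 0.046 with futility stops followed. At 0.425 and 0.85: mean 0.37 and 0.82, slightly low because of futility stops. At 0.85, the mean given an efficacy conclusion is 1.56.

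**Conflict over zero.** Early efficacy stops need P ≤ 0.0147 or smaller, and early futility stops need P > 0.2389 or larger, so a 95% CI cannot disagree with either. Only 0.0440 < P ≤ 0.05 at the final look can produce a conflict: 0.4% under the null, 0.2–0.6% at 1.7, and about 1.5–1.6% at its peak, near a true effect of 0.85.

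**Candidate remedies (SD 3.0).**

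| Case | Ordinary | Median-unbiased, estimate ordering | Repeated CI |
|---|---|---|---|
| Look 2, z = 2.9 | 2.05 (0.66 to 3.44) | 1.91 (0.61 to 3.17) | 0.06 to 4.04 |
| Look 4, z = 1.99, P = 0.0466 | 0.99 (0.02 to 1.98) | 1.02 (0.01 to 2.07) | −0.01 to 2.00 |

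At a true effect of 1.7 the median-unbiased estimate has median 1.70 and its CI covers 95.1%. In the last row it still excludes zero. Because futility stops lower the overall error rate to 0.046, this interval excludes zero from about z = 1.965, below the 2.014 boundary. Only the repeated CI always agrees with the decision.

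**The case against.** The strongest reply is that this is an omission rather than an error. The plan says 95% confidence interval without calling it a fixed-sample one, it lists East 5.3 among its analysis software, and its test is valid. In the look-2 example the adjusted result leads to the same conclusion. Choosing among adjustment methods is partly preference.

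Much of that stands. That the interval is the ordinary one is an inference from silence, and no decision about efficacy changes. But listing software does not select an estimator. Valid methods give different answers, so the choice belongs in the plan before unmasking. The word unbiased in the crossover paragraph is aimed at self-selection into the second phase. It is still not accurate for the reported first-phase estimate under this stopping rule.

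A reader might infer more than the documents support:

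- **That the effect is always overstated.** It is not: bias is zero under the null, and the mean is slightly low at small effects on the SD 3.0 scale.
- **That the CI can contradict an early stop over zero.** The printed boundaries rule that out.
- **That poor coverage among trials stopping at a particular look measures the defect.** For efficacy stops at look 1 (SD 3.0), ordinary coverage is about 66%, but the estimate-ordered interval gives 66.6%. An adjustment of overall coverage is not designed to correct this, so such figures should not be counted.

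**Conclusion.** The point holds as a gap in estimation. At the planned effect, the unadjusted summary averages about 10% too high, or 14–19% too high given an efficacy conclusion, and its 95% CI loses 1.5 to 2.5 percentage points of coverage. The conflict between interval and test is real but rare and confined to the final look. The stronger reading, that the trial's test or type I error is compromised, is not supported: rejection under the null is 0.046 with futility stops followed and about 0.05 if they are ignored.

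The figures assume normal outcomes, 1:1 allocation, looks at exactly 25, 50, 75 and 100% of information, and futility stops that are followed. If futility stops are ignored, coverage at 1.7 is 94.0% and the mean 1.90 (SD 3.0). Dropout and imputation are not modelled.

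**What to change.** Add to the Hypothesis 1 paragraph that:

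1. the primary summary is a median-unbiased estimate with a 95% CI adjusted for the group-sequential design, naming the ordering (ordering by the estimate accommodates the futility boundary);
2. the ordinary ANCOVA least squares difference and CI are shown and labelled as unadjusted;
3. the repeated CI at the stopping look is also given, as the least squares difference ± 3.156, 2.820, 2.440 or 2.014 SE for looks 1 to 4 (a 95.6% CI at the final look, since 1 − 0.0440 = 0.956), and this interval is the one used for consistency with the stopping decision.

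Item 3 is needed because item 1 alone leaves the final-look conflict in place. The crossover paragraph's description of the first-phase effect should be limited to freedom from self-selection.

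The cost is a SAP sentence and a little programming. Sample size, boundaries and data collection do not change. The downsides are a slightly smaller reported effect after an early efficacy stop (2.05 becomes 1.91 in the look-2 example) and a wide, conservative repeated CI, with about 98–99% coverage at the planned effect.

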Randomization will be stratified by institution/hospital and amputation location (upper vs. lower limb) in a 1:1 ratio, and in randomly chosen block sizes. Randomization lists will be created using Statistical Analysis Software computer-generated tables by the University of California San Diego Investigational Drug Service. A randomization list for each enrolling center will be created by the University of California San Diego Investigational Drug Service, and uploaded to a secure, password-protected, encrypted central server. Investigational pharmacists at each institution will prepare all study solution as determined by these randomization lists, accessed by the pharmacists *via* the web-based, secure, password-protected, encrypted central server. Ropivacaine and normal saline are indistinguishable in appearance, and therefore investigators, subjects, and all clinical staff will be masked to treatment group assignment. Unmasking will not occur until statistical analysis is complete (termed "triple masking": subjects, investigators, and statisticians).

Study intervention. Electronic, programmable, portable infusion pumps will be used to administer perineural study solution at fixed rates for over 6 days.³⁶ Electronic, programmable, portable infusion pumps are currently used by the United States Armed Forces and have been used previously by the military to provide CPNB for up to 27 days immediately following limb trauma in soldiers returning from Iraq and Afghanistan.²⁵ Subjects will receive a total of 1,100 mL of study fluid from either one (upper extremity) or two (lower extremity) pump and external reservoir combinations. The continuous basal infusion rate will be determined by catheter location: femoral 2.5 mL/h; popliteal-sciatic 5 mL/h; and infraclavicular 7.5 mL/h (37.5 mg/h for both upper and lower extremity subjects). No patient-controlled bolus dose will be included.

Ambulatory infusion. Prior to discharge, subjects and their caretakers will be provided with verbal and written catheter/pump instructions, the telephone and pager numbers of an investigator available at all times, and a copy of the Institutional Review Board-approved consent form. Subjects with a lower extremity

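### Aim 2a, which gates 2b and 2c, has an unstratified rank test and an imbalance-triggered regression, and the plan does not say which one decides

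*Combined protocol and SAP*

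**What the plan says.** All of this is in section 9 of the combined protocol and SAP.

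- **Randomization** (Treatment group assignment): "Randomization will be stratified by institution/hospital and amputation location (upper vs. lower limb) in a 1:1 ratio". Study Design lists five centers, so there are up to 10 strata.
- **Aim 2a test** (Hypothesis 2a): the groups are compared on the "Patient Global Impression of Change Scale) at 4 weeks using the Mann-Whitney test". Neither site nor limb is mentioned.
- **Adjustment** (next sentence): "Proportional odds logistic regression will be used to adjust for any imbalanced baseline variables, as appropriate".
- **Imbalance rule** (opening of the Statistical Plan): a variable counts as balanced if its standardized difference, the "difference in means or proportions divided by the pooled standard deviation) is less than" √(2/n), where n is the per-group size. The rule covers baseline demographic and pain variables, which are not listed.
- **Gate** (Type I error): "We will use a parallel gatekeeping procedure to control the study-wide type I error at 0.05". The order is "ordered sets, as Aim 1, Aim 2a, Aim 2b and then Aim 2c", and testing moves "to the next set if and only if at least one outcome in the current set reaches significance".

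Set 2a holds one outcome, so its result alone decides whether 2b and 2c are tested.

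**The concern.** A gatekeeping procedure needs one defined p-value for each hypothesis. For 2a the plan names two methods and gives no rule for which result counts. The second method comes into play through a limit that sound randomization will often exceed by chance, and the qualifier *as appropriate* leaves room for judgement on top of that.

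Separately, site and limb were built into the randomization but left out of the 2a analysis. If either predicts global improvement, an unstratified test overstates the error variance and gives up power. At stake are the clarity of the gate to 2b and 2c and some efficiency for 2a. The primary aim's sample size is not affected.

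**Working it through.** **Plan's own figure.** The documents give no power or sample size for 2a. The Aim 1 figure supplies n and can be reproduced. SD of change = √(2 × 3.0² × (1 − 0.50)) = 3.0. The fixed design needs 2 × (3.0 × (1.960 + 1.282)/1.7)² = 65.4 per group. A four-look gamma(−4)/gamma(−2) design with non-binding futility inflates this by 1.091, to 71.4, which rounds up to the stated 72 per group (144 total).

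**The imbalance limit.** With 72 per group the limit is √(2/72) = 0.167. Under randomization the standard error of a standardized difference is √(1/72 + 1/72) = 0.167. The limit is therefore one standard error at any n:

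- P(one variable flagged by chance) = 2 × (1 − Φ(1)) = 0.317.
- At least one of 5 flagged, if independent: 1 − 0.683⁵ = 0.85. At least one of 10: 1 − 0.683¹⁰ = 0.98.
- With pairwise correlation 0.5 these fall to 0.77 and 0.93.

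The counts of 5 and 10 and the correlation are assumptions. The 0.317 does not apply to site and limb, because stratified blocks tend to keep those balanced; the trigger would seldom bring them in.

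**What it does to the 2a test.** This was simulated with N = 144, ten strata and a 7-category outcome. Everything else is assumed: stratum sizes from 8 to 40; 5 or 10 independent baseline covariates, each with log-odds coefficient 0.3; normal stratum effects with SD 0, 0.7 or 1.0; and a treatment log odds ratio of 0 or 0.9. *Switch* means the regression replaces the Mann-Whitney test whenever a covariate is flagged. *Either* means significance on either test opens the gate. *Disagree* means the two p-values fall on opposite sides of 0.05.

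| Scenario | Mann-Whitney | Switch | Either | Disagree | van Elteren |
|---|---|---|---|---|---|
| Null, stratum SD 0, 5 covariates | 0.047 | 0.042 | 0.058 | 0.028 | 0.046 |
| Null, SD 0.7, 5 covariates | 0.038 | 0.036 | 0.049 | 0.023 | 0.051 |
| Null, SD 0.7, 10 covariates | 0.042 | 0.038 | 0.057 | 0.034 | 0.054 |
| Effect, SD 0, 5 covariates | 0.80 | 0.82 | 0.85 | 0.08 | 0.79 |
| Effect, SD 0.7, 5 covariates | 0.72 | 0.76 | 0.79 | 0.10 | 0.76 |
| Effect, SD 1.0, 5 covariates | 0.71 | 0.71 | 0.75 | 0.09 | 0.77 |

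The Monte Carlo standard error is about 0.004 for the null rows and 0.01 for the effect rows.

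- **Omitting the strata.** The Mann-Whitney test rejects in 0.038 to 0.042 of null trials with stratum SD 0.7. It loses 0.764 − 0.723 = 0.04 in power at SD 0.7 and 0.769 − 0.709 = 0.06 at SD 1.0. With no stratum effect it is about 0.01 ahead. A second set of runs with its own assumed stratum sizes and effects gave size 0.030 to 0.038 and a loss of about 3 to 7 points.
- **Ambiguous gate.** The two tests disagree in 2.3% to 3.4% of null trials and 8% to 10% of trials with an effect. The *either* rule has type I error 0.049 to 0.058.

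**The case against.** The strongest objection is that *as appropriate* can naturally mean substitution: Mann-Whitney if the groups are balanced, adjusted regression if not. That gives one p-value. It also resembles Aim 1, where imbalanced variables enter a single analysis of covariance. This stands to the extent that a reader should not infer that two competing p-values will nearly always exist. The documents do not say so, and the 85% and 98% figures describe how often the trigger fires under an assumed variable count and independence. What remains is that the text does not say which reading is meant.

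A reader might also infer that the test could be picked after seeing the outcome. The trigger is a numerical rule on baseline data, and the statisticians stay masked until the analysis is complete. The discretion lies in *as appropriate* and in the open covariate list.

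The strata argument is about efficiency. The documents give no evidence that site or limb predicts global impression of change, and the gain disappears if neither does. Nor is the gap peculiar to 2a: Aim 1 uses the same trigger, and neither Aim 1 nor 2c names the strata. Aim 2a differs in naming two methods without saying which one governs.

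**Conclusion.** The point holds as a minor but concrete defect. The decisive test for 2a is not fixed, and the randomization strata are left out of it.

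Two stronger readings are tempting and should not be drawn. One is that the unstratified Mann-Whitney test is invalid. It is valid, and it is conservative when the strata are prognostic. The other is that study-wide error control fails materially. Under the substitution reading the simulated type I error was 0.036 to 0.042. Even if either p-value could open the gate it was about 0.05 to 0.06, and 2a is reached only after Aim 1 succeeds.

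The likely cost is a few power points for 2a if site or limb is prognostic (about 3 to 7 under assumed stratum SDs of 0.7 to 1.0), and essentially none otherwise. There is also an avoidable dispute over the gate, possible in roughly one trial in ten when treatment works. The 0.317 follows from the plan's own rule. The power, error and disagreement figures rest on assumed stratum sizes, stratum effects, covariate effects and treatment effect.

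**What to change.** Under Hypothesis 2a, name one decisive test that accounts for the randomization strata. Either of these would do:

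- a van Elteren (stratified Mann-Whitney) test by site and limb; or
- proportional-odds regression on treatment, limb, site and baseline average phantom-pain NRS.

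Fix a small-site pooling rule before unmasking. Label the other method a sensitivity analysis, state that it has no role in the gate, and remove the imbalance trigger and *as appropriate* for 2a. The general clause on alternative methods, which covers all analyses, should be worded so that it does not reopen the choice for 2a.

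This takes a sentence or two and needs no new data or change in sample size. The costs are about one power point if the strata turn out not to be prognostic and, if the regression is chosen, reliance on proportional odds, which the rank-test sensitivity analysis would help to check.

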chronic pain clinical trials by the Initiative on Methods, Measurement, and Pain Assessment in Clinical Trials (IMMPACT) consensus statement.⁷⁸ *The primary end point will be the difference in average daily phantom pain intensity at baseline and 4 weeks following the initial infusion (measured with the Numeric Rating Scale as part of the Brief Pain Inventory).*⁷⁹ The primary analyses will compare the two treatments (inter-subject comparisons) during the initial perineural infusion in which half of the subjects will receive active drug (ropivacaine 0.5%), and the other half placebo (normal saline).

Endpoints will be evaluated at baseline and on the day following catheter insertion (Day 1; during infusion); as well as 7, 14, 21, 28 days following the initial catheter insertion (Table 1). These same time points will be evaluated following the second (crossover) catheter insertion begun 4-6 weeks after the initial catheter insertion. Subjects will also be evaluated 6 months and then 1 year after the initial infusion to evaluate longer-term treatment effects.

The questionnaire will differentiate among multiple dimensions of limb pain:

Residual limb ("stump") pain:	painful sensations localized to the portion of limb still physically
	present. ^{80,81}
Phantom limb sensations:	non -painful sensations referred to the lost body part. ^{80,81}
Phantom limb pain:	painful sensations referred to the lost body part. ^{80,81}

Each type of pain/sensation will be defined for subjects immediately prior to questionnaire application at each time point, and subjects will be instructed to specifically address phantom limb pain when responding to the various questions. In addition, since there is a strong correlation between phantom and residual limb pain, we will specifically assess so-called "stump" pain as well. Each time the questionnaire is applied, subjects will be instructed to respond for the previous 3 days (e.g., worst pain during the previous 3 days) because studies have suggested that patients have "increasing difficulty actually remembering symptom levels beyond the past several days."⁸² Exceptions will be on Day 1 for both the initial and crossover treatments that occur during the perineural infusions themselves, because at these time points the interest is in subjects' experiences with the infusion, and not prior to catheter insertion. During these two days, subjects will be instructed to respond for the previous 24 hours.

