Hypothesis 2c. Analysis of covariance adjusting for baseline score will be used to assess the treatment effect of ambulatory CPNB versus placebo on depression at 4 weeks after randomization as measured by the Beck Depression Inventory.

Blinding assessment. We will assess the quality of the blinding of subjects to initial treatment assignment by comparing the randomized groups on the proportion guessing correctly at 4 weeks (after measuring primary outcome pain scores) as to which group they were originally assigned; a Pearson's chi-square test will be used.

For all analyses, alternative statistical methods will be used if the assumptions of the planned analyses are not met. For instance, t-tests or regression analyses on the change or percent change from baseline (depending on which is less correlated with baseline score) will be used instead of analysis of covariance when comparing groups on the 4-week outcomes if the treatment group-by-baseline interaction is significant. Transformations of the data or Mann-Whitney test or other non-parametric procedures will be used if the assumptions of normality and/or equal variances are not met.

Crossover phase. Beginning 4-6 weeks after the original randomization, requesting subjects will receive the opposite treatment from that received in their original randomization, and the same measurements will be collected through 28 days (see Table 1). This option will allow all subjects the opportunity to receive the study treatment. Although a completely unbiased assessment of the average causal effect will not be possible for this

phase because the second treatment will be voluntary, and crossover will thus likely be requested more often from those receiving placebo in the first phase, we will still descriptively report the average treatment effect from those choosing to cross over (but no testing will be done; unbiased average causal effect will be obtained from the first phase).

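### Hypothesis 2b names no baseline adjustment for the seven BPI interference items, in either the joint model or the item-by-item fallback; the result is valid but less precise than it need be

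*Combined protocol and SAP*

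**What the plan says.** All references are to section 9, mostly under Statistical Plan and Data Analysis.

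- **Hypothesis 2b.** The arms are compared at 4 weeks on the seven interference items using a "mixed effects multivariate model (random subject term, fixed treatment effect, unstructured correlation matrix"). The model first tests whether the treatment effect varies by item. "In presence of an interaction, each measure will be evaluated univariably"; otherwise one overall treatment effect is reported. Neither route mentions a baseline score, a change score or adjustment for imbalance.
- **Hypothesis 1.** Analysis of covariance on baseline pain and any imbalanced baseline variables. The extension reads "Similar analyses will be conducted for the secondary outcomes of current/present, worst and least phantom pain", and then adds residual limb pain. The interference items are not in that list.
- **Hypothesis 2a.** A Mann-Whitney test, after which "Proportional odds logistic regression will be used to adjust for any imbalanced baseline variables, as appropriate".
- **Hypothesis 2c.** "Analysis of covariance adjusting for baseline score will be used to assess the treatment effect".
- **Alternative methods.** Analyses of change or percent change "will be used instead of analysis of covariance when comparing groups on the 4-week outcomes if the treatment group-by-baseline interaction is significant".
- **Outcome measurements.** "Endpoints will be evaluated at baseline and on the day following catheter insertion", so baseline interference scores are planned data.
- **Type I error.** The level passed to a later set is multiplied by a factor "equal to the cumulative product of the proportion of significant tests across the preceding sets", with Bonferroni correction within a set.

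**The concern.** Of the four hypotheses, 2b is the only one for which the plan names no covariate. Chronic pain scores usually correlate with their own baseline, and the plan itself assumes 0.50 for the pain NRS. A 4-week comparison that ignores baseline leaves that between-patient variation in the error term.

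Hypothesis 2b carries the trial's claim about physical and emotional functioning. Lost precision would matter most in three places: effects below 1.7 points, single-item tests at a Bonferroni level, and a trial that stops at an interim look. It could also reach Hypothesis 2c, because the share of significant 2b tests sets the level at which 2c is tested.

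The wording also leaves the analyst a choice. Two statisticians could follow it and fit different models: no baseline, own-item baseline or mean baseline.

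**Working it through.** **The plan's own figure.** Sample size considerations gives a 1.7-point difference, SD 3.0, correlation 0.50, two-sided 0.05, power 0.90 and four looks. A fixed design needs 2 × (1.960 + 1.282)² × 3.0² / 1.7² = 65.4 per arm. Numerical integration over the stated boundaries gives an inflation factor of 1.095, so 65.4 × 1.095 = 71.6, or 72 per arm (N=144). The plan's figure reproduces. It concerns the primary outcome only; no power, SD or correlation is given for 2b.

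**Single item.** Adjusting for baseline with correlation ρ multiplies the variance by 1 − ρ². The equivalent increase in patients is 1/(1 − ρ²) − 1.

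| ρ | Variance factor | Equivalent extra patients |
|---|---|---|
| 0.3 | 0.91 | 10% |
| 0.5 (borrowed from the NRS) | 0.75 | 33% |
| 0.7 | 0.51 | 96% |

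With an assumed item SD of 3.0 and 72 per arm, the SE is 3.0 × √(2/72) = 0.500 unadjusted and 0.500 × √0.75 = 0.433 adjusted. At a level of 0.05/7 (critical value 2.690), power is 25% versus 35% at 1.0 point and 76% versus 89% at 1.7 points.

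**Overall effect across seven items.** Assumptions: item SD 3.0, inter-item correlation 0.6 at one visit, same-item correlation over time 0.5, cross-item correlation over time c = 0.2, 0.3 or 0.4.

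- Variance of the seven-item mean: 3.0² × (1 + 6 × 0.6)/7 = 3.0² × 4.6/7.
- Unadjusted SE at 72 per arm: 3.0 × √(2/72) × √(4.6/7) = 0.405.
- Correlation R of baseline and 4-week means: (0.5 + 6c)/4.6.
- Adjusted SE: 0.405 × √(1 − R²).
- Effect detectable with 90% power: 3.242 × SE.

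| | No baseline | c = 0.2 | c = 0.3 | c = 0.4 |
|---|---|---|---|---|
| R | – | 0.370 | 0.500 | 0.630 |
| SE | 0.405 | 0.377 | 0.351 | 0.315 |
| Equivalent extra patients | – | 16% | 33% | 66% |
| 90%-power effect (points) | 1.31 | 1.22 | 1.14 | 1.02 |
| Power at 1.0 point | 69% | 76% | 81% | 89% |
| Power at 1.7 points | 98.7% | 99.5% | 99.8% | >99.9% |

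**Simulation check.** In 10,000 simulated trials per value of c, with an estimated unstructured covariance and mean baseline as the only covariate, the gains were 14%, 32% and 65%. Power at 1.0 point was 70% versus 76%, 81% and 88%. Estimates were unbiased.

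**Early stopping.** Nominal power for the overall effect at 1.7 points, not conditioned on crossing a boundary:

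| Total N | No baseline | c = 0.2 / 0.3 / 0.4 |
|---|---|---|
| 72 (second look) | 84% | 89% / 93% / 97% |
| 100 (plan's expected size under the alternative) | 94% | 96% / 98% / 99% |
| 108 (third look) | 95% | 97% / 99% / 99.7% |

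**Gate to 2c.** 200,000 draws per scenario, with known covariance, Aims 1 and 2a taken as passed at full level, interim looks ignored, the interaction tested at 0.05 and items at 0.05/7. Adjustment is mean baseline in the joint model and own-item baseline in the fallback.

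- Item effects 1.1 to 2.3: the gate opens 99.3% versus at least 99.8% of the time; mean 2c level 0.039 versus 0.043.
- Item effects 0.4 to 1.6: it opens 80% versus 86%, 90% and 94%; mean 2c level 0.021 versus 0.025 to 0.027.

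**The case against.** **No error is shown.** An unadjusted comparison of randomized arms is valid, and this is a secondary hypothesis. That stands and caps the weight of the point.

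**The plan may already intend adjustment.** The alternative-methods paragraph applies to all analyses and treats analysis of covariance as the usual method for 4-week outcomes. The parenthesis describing the 2b model need not list every covariate. This is a fair reading, and the gap may be only one of wording. But the clause is a conditional replacement rule and does not say how baseline enters a seven-item model, so the sentence is needed either way.

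**The contrast with 2a is thin.** Its main test is unadjusted, adjustment is only for imbalance, and a global impression of change has no baseline value. This stands: the real comparison is with Hypotheses 1 and 2c.

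**The sizes rest on assumed inputs.** This stands, in both directions. Inter-item correlation 0.8 with c = 0.2 gives a 9% gain (power at 1.0 point 59% versus 63%). Inter-item 0.5 with c = 0.4 gives 111%. With item SD 2.0 and inter-item 0.6, power at 1.0 point is already 96% unadjusted, against 98% to 99.8%.

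**N=100 is an average, not a look.** Correct. The figures at 72 and 108 are the better guide, and they show the same pattern.

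**The gate scenarios are invented, and the shift in mean 2c level is only 0.004 to 0.006.** Also correct; the gate is a minor argument.

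**Conclusion.** The concern holds. The plan names no baseline term for 2b on either route, and no other text clearly supplies one. The consequence is lost precision, not bias: type I error, the primary aim and N=144 are untouched.

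For one item the loss equals 33% more patients if the NRS correlation of 0.50 applies, and 10% to 96% for correlations of 0.3 to 0.7. For the overall effect it is 16% to 66% under the main assumptions, and 9% to 111% over the wider set tried. With a 1.7-point overall effect at full enrolment the practical difference is about one percentage point of power. It is larger for effects near 1.0 point, for Bonferroni-level single items and after an early stop.

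This is a cheap improvement of low-to-moderate weight that should be made. Confidence is medium, because the documents give no variance or correlation for these items and the intent may already be to adjust.

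**What to change.** Add one sentence to the Hypothesis 2b paragraph, before unmasking: the mixed model includes the patient's mean baseline interference score as a covariate, and when items are analyzed singly each is adjusted for its own baseline score. It would also help to say whether imbalanced baseline variables enter 2b, as they do in Hypotheses 1 and 2a.

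Own-item baselines (a baseline-by-item term) may be added to the joint model but are not needed for the overall effect. They sharpen the treatment-by-item test, so 2b goes to single-item testing more often. With item effects of 0.4 to 1.6, the interaction is declared 70% of the time with no covariate or the mean only, and 98%, 84% and 74% with own-item plus mean (c = 0.2, 0.3, 0.4). The mean 2c level is then 0.020, 0.023 and 0.027, slightly below the unadjusted 0.021 at c = 0.2. Under the exchangeable correlations assumed here, the mean score alone leaves the interaction test unchanged.

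Cost: no new data. The joint model gains one slope (up to eight if own-item baselines are added), and each item-level analysis gains one.
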